## 4. PARTICIPANT SELECTION

### 4.1 Inclusion Criteria

- Premenopausal women
- 21-54 years of age
- No change in menstrual patterns for the past 6 months preceding the time of registration
- Have a BMI of 25 kg/m^2 or greater
- Large waist circumference
  - ≥ 88 cm (≥35 inches) or
  - ≥ 80 cm (≥31 inches) for Asian Americans, individuals with polycystic ovary syndrome, or individuals with non-alcoholic fatty liver disease
- Have at least one other component of metabolic syndrome (103) reported below:
  - Elevated triglycerides (≥ 150 mg/dL (1.7 mmol/L)) or on drug treatment for elevated triglycerides
  - Reduced HDL-C (< 50 mg/dL (1.3 mmol/L)) or on drug treatment for reduced HDL-C
  - Elevated blood pressure (≥ 130 mm Hg systolic blood pressure or ≥85 mm Hg diastolic blood pressure) or on antihypertensive drug treatment in a patient with a history of hypertension
  - Elevated fasting glucose (≥100 mg/dL)

- Mammogram negative for breast cancer within the 12 months preceding the time of registration for women  $\geq 50$  years of age
- Ability to understand and the willingness to sign a written informed consent document

#### **4.2 Exclusion Criteria**

- Postmenopausal women
  - Amenorrhea for at least 12 months (preceding the time of registration), or
  - History of hysterectomy and bilateral salpingo-oophorectomy, or
  - At least 55 years of age with prior hysterectomy with or without oophorectomy, or
  - Age 35 to 54 with a prior hysterectomy without oophorectomy OR with a status of ovaries unknown with documented follicle-stimulating hormone level demonstrating elevation in postmenopausal range
- Women who are pregnant, planning pregnancy within the next year, or lactating/breastfeeding
- On treatment with any drug for diabetes
- Have uncontrolled intercurrent illness including, but not limited to, ongoing or active infection, symptomatic congestive heart failure, unstable angina pectoris, cardiac arrhythmia, or any illness that would limit compliance with study requirements
- Have received chemotherapy and/or radiation for any malignancy (excluding non-melanoma skin cancer and cancers confined to organs with removal as only treatment) in the past 5 years (preceding the time of registration)
- Have received other investigational agents within the past 3 months (preceding the time of registration)
- Have a history of lactic acidosis or risk factors for lactic acidosis
- Have renal disease or dysfunction (creatinine  $\geq 1.4$  mg/dL)
- Have hepatic dysfunction (bilirubin  $> 1.5$  x ULN unless with Gilberts syndrome or AST/ALT  $> 3$  x ULN)
- Have a history of alcoholism or high alcohol consumption (average of  $> 3$  standard drinks/day)
- Have a history of allergic reactions to metformin or similar drugs
- Have a history of severe claustrophobia
- Have electrically, magnetically, or mechanically activated implants including cardiac pacemaker, cochlear implants, magnetic surgical clips or prostheses
- Have breast implants

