Grade 3 events possibly, probably, and definitely related to study agent, and Grade 4 events regardless of relationship to study agent, will result in permanent withdrawal of study agent. Subjects will be followed for resolution of adverse events. The Principal Investigator and Medical Director will be notified immediately of any grade 3 or 4 adverse events. The study investigators will decide if the adverse event is related to the agent.

All AEs, including lab abnormalities will be followed for 2 weeks or longer for resolution according to good medical practices and documented as such.

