## 11. Description and Reporting of Adverse Events

### 11.1 Adverse Events

An adverse event (AE) is any untoward medical occurrence in a study participant. An AE does not necessarily have a causal relationship with the treatment or study participant. An AE can therefore be any unfavorable and unintended sign (including a clinically significant abnormal laboratory finding), symptom, or disease temporally associated with participation in a study, whether or not related to that participation. This includes all deaths that occur while a participant is on a study.

A list of adverse events that have occurred or might occur (Reported Adverse Events and Potential Risks) can be found in Section 6.2, Pharmaceutical Information as well as the package insert.

All adverse events that occur after the informed consent is signed must be recorded whether or not related to study agent. All adverse events will be entered into the OnCore database.

AE Data Elements include:

- AE reported date
- AE Verbatim Term
- Common Terminology Criteria for Adverse Events v4.0 (CTCAE) AE term
- Event onset date and event ended date
- Severity grade
- Attribution to study agent (relatedness)
- Whether or not the event was reported as a Serious Adverse Event (SAE)
- Whether or not the subject dropped due to the event
- Action taken with the study agent
- Outcome of the event
- Comments

All AEs will be assessed according to CTCAE Version 4  
 (<http://ctep.cancer.gov/protocolDevelopment/electronicapplications/docs/ctcaeV4.pdf>).

AEs that do not have a corresponding CTCAE term will be assessed according to the general guidelines for grading used in the CTCAE v4.0 as stated below.

Grade	Severity	Description
1	Mild	Mild; asymptomatic or mild symptoms; clinical or diagnostic observations only; intervention not indicated.
2	Moderate	Moderate; minimal, local or noninvasive intervention indicated; limiting age-appropriate instrumental ADL*.
3	Severe	Severe or medically significant but not immediately life-threatening; hospitalization or prolongation of hospitalization indicated; disabling; limiting self care ADL**.
4	Life threatening	Life-threatening consequences; urgent intervention indicated.
5	Fatal	Death related to AE.

Activities of Daily Living (ADL)

\*Instrumental ADL refer to preparing meals, shopping for groceries or clothes, using the telephone, managing money, etc.

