\*\*Self care ADL refer to bathing, dressing and undressing, feeding self, using the toilet, taking medications, and not bedridden.

The possibility that the adverse event is related to study agent will be classified as one of the following: not related, unlikely, possible, probable, definite.

All AEs, including lab abnormalities that in the opinion of the investigator are clinically significant, will be followed according to good medical practices and documented as such.

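### Newly detected diabetic-range glucose at screening does not bar entry: diabetes is excluded by name only when drug-treated, and the fasting glucose item has no upper limit

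*Combined protocol and SAP*

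**What the plan says.** The exclusion list in section 4.2 mentions diabetes once: "On treatment with any drug for diabetes". Section 4.1 requires a large waist and at least one further component of metabolic syndrome out of four: triglycerides, HDL cholesterol, blood pressure or glucose. The glucose component reads "Elevated fasting glucose (≥100 mg/dL", with no upper bound.

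Two general exclusions in 4.2 could bear on the case: "Have uncontrolled intercurrent illness including, but not limited to, ongoing or active infection" (the item continues with cardiac examples and any illness limiting compliance) and "Have a history of lactic acidosis or risk factors for lactic acidosis".

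Under section 7.2, consent comes first. Every screened woman then has fasting blood drawn for a comprehensive metabolic panel (CMP) and lipids, and this draw may be repeated when clinically indicated. Final eligibility is assessed at baseline (section 7.1), followed by randomisation to metformin or placebo for 12 months (sections 3 and 5.1). Section 5.4 bars metformin from outside the study and other biguanides.

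**The concern.** Section 6.1 states that the study agent is indicated for type 2 diabetes. The trial recruits overweight or obese women with metabolic components, and raised glucose is itself a route to entry, so some screening panels may reveal diabetes that nobody knew about. On the written criteria such a result does not stop randomisation and may even be what qualifies the woman. She may then be assigned placebo for a year. What is at stake is the safety of individual participants, not the validity of the treatment comparison.

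**Working it through.** The plan gives no figure on this point and no arithmetic applies. The check is to follow one case through the written rules: a woman with no history of diabetes, on no diabetes drug, whose screening panel returns a fasting glucose in the diabetic range. One assumption is needed. The documents do not list the contents of the CMP; I take it to report glucose, because no other scheduled screening test would supply the value for the 4.1 item.

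1. **Inclusion (4.1).** Suppose she meets the age, menstrual, BMI and waist criteria. Her glucose is above 100 mg/dL, so it satisfies the metabolic component. Had she qualified on triglycerides, HDL cholesterol or blood pressure instead, her glucose would not enter the decision at all. Either way, no ceiling applies.

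2. **The exclusion that names diabetes (4.2).** It depends on current drug treatment. She takes none, so it does not apply. If she starts a diabetes drug between screening and baseline, the final eligibility assessment would exclude her, but nothing visible requires that step.

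3. **Uncontrolled illness (4.2).** The item is open-ended, so an investigator could apply it to overt, uncontrolled diabetes. It names neither diabetes nor a glucose value, so two investigators could decide the same result differently.

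4. **Risk factors for lactic acidosis (4.2).** The term is not defined. Section 6.2 names diabetes mellitus among conditions associated with lactic acidosis, which supports a wide reading. But if the item covered all diabetes, the separate line on drug-treated diabetes would have no work left to do. The contraindications in 5.3 do not list diabetes either.

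5. **Repeat screening blood (7.2).** The repeat is permitted, not required, and no rule says what follows from a confirmed high value.

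6. **Adverse event provisions.** Section 11.1 states: "All adverse events that occur after the informed consent is signed must be recorded whether or not related to study agent". Its definition of an adverse event includes clinically significant laboratory abnormalities, and consent precedes the screening draw, so the result could be recorded. Section 5.5 adds: "All AEs, including lab abnormalities will be followed for 2 weeks or longer for resolution according to good medical practices". Section 11.1 has a similar sentence: "All AEs, including lab abnormalities that in the opinion of the investigator are clinically significant, will be followed according to good medical practices". These rules govern recording and follow-up, not eligibility. Whether a state already present at screening counts as an adverse event is itself a judgment.

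7. **Final eligibility (7.1).** This step applies the same criteria and so carries the same gap.

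Result: no written criterion necessarily excludes her. Steps 3 to 6 give an investigator discretion to act; none sets a limit or makes action before randomisation mandatory.

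**The case against.** The strongest reply is that the protocol leaves a clinical matter to clinicians and gives them enough to work with. Two mandatory exclusions can be read to cover the case, the blood draw can be repeated, and abnormal results must be followed under good medical practice. The visits at months 3, 6 and 9 review vital signs, medication and side effects. Placebo is added to usual care: 5.4 leaves other glucose-lowering drugs open. Admitting women with raised glucose is a deliberate choice in a metabolic syndrome trial.

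Most of this stands, and it is why the gap is modest. It does not close the gap, because a careful investigator following the text exactly may still randomise the woman.

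Several stronger readings are tempting and are not supported:

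- *All untreated diabetes should be excluded, including known diet-managed diabetes.* A woman with known diet-managed diabetes already has a diagnosis and management. The documents show no harm to her from placebo.
- *The numeric limits on renal and hepatic function show that a glucose limit was overlooked.* Those limits correspond to the contraindications in 5.3. Raised glucose is not a contraindication; type 2 diabetes is the agent's indication.
- *Section 4.1 already obliges the site to check glucose.* It does not: glucose is one of four alternatives. The value comes from the panel drawn on every screened woman.
- *Placebo means a year without treatment.* Section 5.4 contradicts this.
- *The trial departs from a non-diabetic population.* The rationale in 2.1 speaks of non-diabetics, but the objective in section 1 specifies metabolic syndrome only.
- *Women will not be told the result.* Consent pages are not part of this copy, so notice of results may be provided there.

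**Conclusion.** The point holds for newly detected diabetic-range glucose at screening, and only for that. The criteria as written allow such a woman to be randomised to placebo for 12 months, with any action beforehand left to the investigator's judgment.

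The documents give no prevalence of undetected diabetes among otherwise eligible women, so the number affected cannot be estimated and could be zero. No effect on the breast density endpoint or any other endpoint is claimed. The conclusion rests on the visible text and on the assumption that the screening panel reports glucose. This is a change to consider, not a defect that undermines the trial.

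**What to change.** Keep the current 4.2 line on drug-treated diabetes and add an exclusion along these lines: *Screening fasting glucose at or above the diagnostic threshold for diabetes (value to be stated by the sponsor), confirmed by the repeat draw allowed in 7.2.* The sponsor must supply the value, because the documents give only the 100 mg/dL floor. Add to 7.2: *Women excluded for this reason will be told the result and referred for care*, unless the consent form already provides for this.

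The first result comes from blood already drawn, and the repeat is already permitted. No new on-study test, visit or analysis is needed. The cost is a repeat draw for women with a high first value, and a few screened women (number not estimable) who become ineligible and are replaced before randomisation. The planned 150 (75 per arm) does not change; the population becomes slightly narrower.

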## **5. AGENT ADMINISTRATION**

### **5.1 Dose Regimen and Dose Groups**

- Subjects will be randomly assigned to the following treatment groups:
  - Metformin, 850 mg tablets
  - Placebo tablets
- Duration of treatment is 12 months ( $52 \pm 4$  wks).

### **5.2 Study Agent Administration**

- For the first four weeks, 1 metformin or placebo tablet will be taken daily.
- For the remaining treatment period, 2 metformin or placebo tablets will be taken daily. Depending on the tolerability, 2 tablets may be taken together with a meal or taken separately (i.e., one tablet twice a day).

- Tablets should be taken with food, preferably with the evening meal.
- Tablets should be swallowed with a full 8 oz glass of water.

### **5.3. Contraindications**

Metformin is contraindicated in patients with

- Renal disease or renal dysfunction
- Known hypersensitivity to metformin hydrochloride
- Acute or chronic metabolic acidosis
- Hepatic impairment, as defined in the exclusion criteria

Because use of iodinated contrast materials may result in acute alteration of renal function and have been associated with lactic acidosis in patients receiving metformin, patients who plan to undergo radiologic studies involving intravascular administration of iodinated contrast materials will not be permitted to begin study medication until at least 48 hours following the procedure and only after renal function has been re-evaluated and found to be normal (serum creatinine < 1.4 mg/dL).

### **5.4 Concomitant Medications**

Participants may not use non-study metformin or other biguanides while on study.

Cationic drugs (e.g., amiloride, digoxin, morphine, procainamide, quinidine, quinine, cimetidine, ranitidine, triamterene, trimethoprim, or vancomycin) have the potential for interaction with metformin by competing for common renal tubular transport systems which may interfere with the disposition of metformin. Although such interactions remain theoretical (except for cimetidine), careful patient monitoring is recommended in patients who are taking cationic medications that are excreted *via* the proximal renal tubular secretory system.

All medications (prescription and over-the-counter), vitamin and mineral supplements, and/or herbs taken by the participant will be documented on the concomitant medication CRF and will include: 1) start and stop date, dose and route of administration, and indication. Medications taken for a procedure (e.g., biopsy) should also be included.

If a subject requires a radiologic exam involving intravascular administration of iodinated contrast materials while participating in the study, she must discontinue study agent for at least 48 hours prior to having the exam and will not be permitted to restart study medication until at least 48 hours following the procedure and only after renal function has been re-evaluated and found to be normal (serum creatinine < 1.4 mg/dL).

### **5.5 Dose Modification**

The NCI Common Terminology Criteria for Adverse Events (CTCAE) Version 4 will be used for toxicity reporting. For grade 1 adverse events or less, no dose modification will be made.

For grade 2 adverse events probably or possibly related to study agent persisting for more than three days during the first 4 weeks of dosing with 1 tablet of 850 mg metformin or placebo daily, study drug will be held. Study drug will be reintroduced at the same dose when the adverse event resolves to Grade 1 or below within 2 weeks. If the Grade 2 event does not resolve to Grade 1 or below within 2 weeks, participants will be removed from the study and followed for resolution of the adverse event.

For grade 2 adverse events probably or possibly related to study agent persisting for more than three days after taking 2 tablets of 850 mg metformin or placebo daily, study drug will

be held. Study drug will be reintroduced at 50% dose (1 tablet of 850 mg metformin or placebo daily) when the adverse event resolves to Grade 1 or below within 2 weeks. If the Grade 2 event does not resolve to Grade 1 or below within 2 weeks, participants will be removed from the study and followed for resolution of the adverse event. After reinstatement of 50% dose (1 tablet of 850 mg metformin or placebo daily) for a minimum of 2 weeks, the full dose (2 tablets of 850 mg metformin or placebo daily) may be reintroduced at the discretion of the study physician. If the Grade 2 adverse event recurs and persists for more than three days following reinstatement of the full dose and is considered definitely, probably or possibly related to study agent, the study agent will be held and reintroduced at 50% dose (1 tablet of 850 mg metformin or placebo daily) if the adverse event resolves to Grade 1 or below within 2 weeks. The dose will then be kept at the reduced dose for the duration of the study. If the Grade 2 event does not resolve to Grade 1 or below within 2 weeks, participants will be removed from the study and followed for resolution of the adverse event. If participants do not wish to be re-challenged with the full dose, they may remain on study at 50% dose.

For Grade 2 or Grade 3 adverse events not considered related to study agent, the study agent may be stopped and resumed at the discretion of study physician.

Grade 3 events possibly, probably, and definitely related to study agent, and Grade 4 events regardless of relationship to study agent, will result in permanent withdrawal of study agent. Subjects will be followed for resolution of adverse events. The Principal Investigator and Medical Director will be notified immediately of any grade 3 or 4 adverse events. The study investigators will decide if the adverse event is related to the agent.

All AEs, including lab abnormalities will be followed for 2 weeks or longer for resolution according to good medical practices and documented as such.

## **6. PHARMACEUTICAL INFORMATION**

### **6.1 Metformin**

Metformin is a biguanide indicated as an adjunct to diet and exercise to improve glycemic control in adults and children with type 2 diabetes mellitus. Metformin is one of the most widely used oral antihyperglycemic drugs in the management of type 2 diabetes. It has been used worldwide for over 40 years to treat type 2 diabetes, and was approved in the United States (US) by the Food and Drug Administration (FDA) as an antidiabetic in 1995 (104). It is also used off-label for polycystic ovary syndrome and metabolic syndrome. The major mechanism of metformin action *in vivo* involves suppression of hepatic gluconeogenesis and glucose output, which is associated with a decline in circulating glucose concentration and a secondary decline in insulin levels (105).

Beneficial effects have also been observed in non-diabetics, including treatment of weight gain induced by antipsychotic medications (106), polycystic ovary syndrome (6), nonalcoholic fatty liver (107) and diabetes prevention in high-risk subjects (108). It has a demonstrated safety profile and good tolerability in both diabetics and non-diabetics.

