## 1. OBJECTIVES

The overall objective of this Phase II double-blind, randomized, placebo-controlled trial of metformin is to determine its potential effects on recognized and putative markers of breast cancer risk in overweight or obese premenopausal women who have metabolic syndrome.

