### **6.5 Registration/Randomization**

Subjects will be considered registered on the date they sign the approved informed consent document with a member of the study staff. Randomization will be performed using computer-generated random permuted blocks.

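### Recent metformin use before entry is not excluded, although the protocol recruits women in whom it says the drug is already used off-label, so some baselines may still carry a drug effect.

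*Combined protocol and SAP*

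**What the plan says.** **Prior exposure is foreseeable.** Section 6.1 states: "It is also used off-label for polycystic ovary syndrome and metabolic syndrome". It also lists non-alcoholic fatty liver among the non-diabetic conditions in which benefit has been seen. Section 1 sets the population as "overweight or obese premenopausal women who have metabolic syndrome". The lower waist limit in section 4.1 applies to Asian Americans and to "individuals with polycystic ovary syndrome, or individuals with non-alcoholic fatty liver disease".

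**Two rules touch non-study metformin.**
- Section 4.2 excludes women "On treatment with any drug for diabetes". This is in the present tense and has no look-back.
- Section 5.4 says: "Participants may not use non-study metformin or other biguanides while on study".

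**Timing.** Section 6.5 says: "Subjects will be considered registered on the date they sign the approved informed consent document". Sections 3 and 7.3 have eligible women return for baseline in the midluteal phase when feasible. No minimum time from consent, or from the last metformin tablet, to baseline is given.

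**Look-backs exist for other things.** Section 4.2 uses 3 months for investigational agents and 5 years for chemotherapy or radiation. Section 4.1 asks for 6 months of stable menstrual pattern.

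**Medication history.** Sections 3 and 7.2 collect it at screening. No eligibility rule in 4.2, randomisation provision in 6.5 or model term in 9.1 uses it to identify earlier metformin use.

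**The concern.** Sections 2.1 and 2.3.2 cite studies in which metformin lowered insulin, testosterone and androstenedione and raised sex hormone binding globulin and IGF-BP1 in women with polycystic ovary syndrome. Most of these are secondary endpoints here. A woman who has just stopped the drug may therefore come to baseline with values that are already partly treated.

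Four parts of section 9.1 depend on a clean baseline:
- The cross-sectional correlations of baseline metabolites with density, hormones and cytokines have no control arm, so randomisation does not protect them.
- Within-arm changes would be too small on metformin and would include withdrawal on placebo.
- The time parameter is read as change among placebo women, so rebound after stopping would appear as a placebo effect.
- Restricting the change correlations to the metformin arm is justified by expecting only random variation under placebo. Rebound would contradict that.

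The primary contrast is at stake only if an earlier effect on density lasts through the placebo year.

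**Working it through.** **1. The eligibility rules, for a woman who stopped metformin shortly before consent**

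| Rule | Does it exclude her? |
|---|---|
| 4.2, drug treatment for diabetes | No: she is not on treatment now |
| 4.2, investigational agents, 3 months | No: marketed metformin is not an investigational agent |
| 5.4, biguanides while on study | No: she takes none on study |
| 4.1, stable menstrual pattern, 6 months | No: it does not concern metformin |

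She is eligible. If on study begins at consent, metformin must have ended by then, but nothing sets how long before baseline that is.

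**2. The plan's own figure**

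Inputs from section 9.2: 75 per arm, 20% dropout, two-sided 0.05, 80% power, 0.516 SD.
- Evaluable: 75 × 0.80 = 60 per arm.
- Noncentrality: 0.516 / √(2/60) = 2.826, with 118 degrees of freedom and critical t of 1.980.
- Power is 0.800, and the detectable difference at 80% is 0.5157 SD. The stated 0.516 SD reproduces.

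**3. Sensitivity to recent users**

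The documents give no prevalence, so p, the share of recent users in each arm, is assumed at 5% to 30%. Let d = 0.516 SD be the true effect. Assume that a recent user already carries the whole of d at baseline, and let r be the fraction of it that reverses on placebo by month 12. Mean changes are:
- Metformin arm: −(1 − p)d, because a recent user gains nothing further.
- Placebo arm: +p·r·d.
- Difference: −(1 − p)d − p·r·d = −d[1 − p(1 − r)].

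Mixing users and non-users adds p(1 − p)d² to the variance of the change, in both arms if r = 1 and in the metformin arm only if r = 0.

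At p = 0.10 the added variance is 0.10 × 0.90 × 0.516² = 0.0240.
- Full reversal (r = 1): the difference stays 0.516. SD = √1.0240 = 1.012, the standardised difference is 0.510 and power is 79.1%.
- No reversal (r = 0): the difference is 0.90 × 0.516 = 0.464. SD averaged over arms = √(1 + 0.0240/2) = 1.006, the standardised difference is 0.462 and power is 70.8%. Without the mixture variance it is 71.3%.

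| p (assumed) | Metformin change, SD | Placebo change if r = 1, SD | Power, r = 1 | Difference if r = 0, SD | Power, r = 0 |
|---|---|---|---|---|---|
| 5% | −0.490 | +0.026 | 79.6% | 0.490 | 75.6% |
| 10% | −0.464 | +0.052 | 79.1% | 0.464 | 70.8% |
| 20% | −0.413 | +0.103 | 78.4% | 0.413 | 60.2% |
| 30% | −0.361 | +0.155 | 77.9% | 0.361 | 49.0% |

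At p = 2% even r = 0 leaves 78% power. The same arithmetic serves the hormone endpoints, for which 9.2 also uses 0.516 SD.

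**The case against.** **Current use is probably covered.** Section 2.1 calls metformin an antidiabetic drug, so the exclusion can fairly be read as applying to it whatever the indication. A reader might infer that a woman now taking it for polycystic ovary syndrome could enrol. The wording leaves some doubt, but that is not its natural reading, and 5.4 bars her from continuing. The gap that stands is recent, ended use.

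**Randomisation protects the primary test.** Prior use is balanced between arms in expectation, and the treatment test is the group-by-time term. With full reversal that contrast is unbiased. This objection stands.

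**The harms rest on opposite conditions.** Placebo rebound needs the earlier effect to reverse, while lost power needs it to persist. A reader might infer that the trial suffers both in full, or that its power is really near 71% or 60%. The documents do not support that. The low figures need an assumed prevalence, a full effect at entry and no reversal over 12 months off drug. For density, section 2.2 only hypothesises any metformin effect.

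**Two further inferences fail.**
- A reader might expect former users to be selected for tolerance, so that gastrointestinal events are understated. Section 6.2 reports that diarrhea made 6% of metformin-treated patients stop, so former users may include women who stopped for intolerance. The direction is unknown.
- A reader might expect the metformin-arm change correlations to be weakened. Women with near-zero change in both variables can strengthen a correlation as well as weaken it.

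None of this supplies the missing look-back or protects the uncontrolled baseline and within-arm analyses.

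**Conclusion.** The gap is real. The protocol describes off-label use of its own study drug in the women it recruits, sets look-backs for other prior exposures, and sets none for metformin. A woman who has recently stopped is eligible.

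The analyses most exposed are the baseline cross-sectional correlations, the within-arm changes, the placebo time effect and the assumption that placebo change is random variation. At 10% recent users and full reversal, a placebo change of about +0.05 SD would be withdrawal, and the metformin change would shrink from 0.516 to 0.464 SD.

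No bias in the primary contrast is shown. Power at an assumed 10% lies between about 79% (full reversal) and about 71% (no reversal, an extreme bound). Where the trial falls depends on the share of recent users and on persistence, and the documents give neither. This is worth correcting because the correction is cheap. It does not undermine the design.

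**What to change.** Reword the section 4.2 criterion to exclude metformin or another biguanide taken for any indication, at registration or within a stated look-back before it, and keep the bar on other drug treatment for diabetes. The sponsor should set and justify the length of the look-back. The 3 months used for investigational agents is a precedent for having a window, but it is not evidence for that length with metformin. State whether the window runs to registration or to baseline, and reconcile the wording with 5.4 so that entry and on-study rules cover the same drugs.

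Verify it from the medication history already taken at screening, and say that the history must capture past metformin with its stop date and indication.

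If enrolment is under way, tabulate prior metformin use by arm and add a sensitivity analysis of the primary and hormone endpoints, and of the baseline correlations, without recent users.

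The cost is one criterion and one history item, with no new procedure. The downside is the loss of a number of recent users that is probably small but unknown. A window lessens the problem, but it cannot remove an effect that outlasts it.
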